## 8.11.6. Vaccination or Antibiotic Prophylaxis

All participants must be vaccinated against meningococcal infections within 3 years or before the administration of study intervention on Day 1. Participants who initiate study intervention treatment less than 2 weeks after receiving a meningococcal vaccine must receive treatment with appropriate prophylactic antibiotics until at least 2 weeks after vaccination.

## 8.11.7. Rerandomization

All participants who are determined to be eligible for Study ALXN2050-MG-201 by the Investigator will be randomized to treatment via an IRT system on Day 1 (Section 4.1). Participants randomized to placebo will be further randomized to 1 of the 2 active treatment groups (ie, ALXN2050 120 or 180 mg) at Week 8.

## 9. STATISTICAL CONSIDERATIONS

Statistical methods for this study will be further detailed in a separate statistical analysis plan (SAP). The SAP will be developed and finalized prior to the database lock. Statistical analyses will include tabulations of summary data, inferential analyses, by-participant listings, and figures. Inference from efficacy analyses will be based on a 2-sided type I error rate ( $\alpha$ ) of 10% unless stated otherwise. The summary statistics for continuous variables will include, but not be limited to, the number of participants, mean, standard deviation, minimum, median, and maximum. For categorical variables, frequencies and percentages will be presented.

All efficacy analyses will be based on the Full Analysis Set (FAS). Supplemental per-protocol analyses for primary and secondary efficacy endpoints will be performed based on the Per Protocol Set (PPS) in the same manner as done for the FAS. Safety analyses will be performed on the Safety Set (SS).

The baseline value for analysis and reporting will be based on the last nonmissing measurement on or prior to the first dose of study intervention unless stated otherwise.

Analyses will be performed using the Statistical Analysis System (SAS®) software Version 9.4 or higher.

Given that this is a proof-of-concept Phase 2 study, all results will be interpreted as exploratory in nature.

## 9.1. Statistical Hypotheses

## 9.1.1. Primary Hypothesis

The primary hypothesis is that the ALXN2050 180 mg bid group is superior to the placebo group in the proportions of responders in the primary endpoint. The responders are defined as participants who achieve an MG-ADL total score reduction of at least 2 points in any 4 consecutive weeks during the first 8 weeks of the PEP and who did not receive rescue therapy. The hypothesis for assessing superiority with respect to the proportions of responders is:

 $H_0: p_3 - p_1 \le 0; \ H_1: p_3 - p_1 > 0$ 

Where  $p_1$  and  $p_3$  are the proportions of responders in the primary endpoint for the placebo and ALXN2050 180 mg bid groups, respectively.

## 9.1.2. Secondary Hypotheses

The secondary hypothesis is that there is an increasing trend in the proportions of responders in the primary endpoint among the 3 treatment groups. The hypothesis for assessing the increasing trend is:

 $H_0: p_1 = p_2 = p_3; H_1: p_1 \le p_2 \le p_3$ ; with at least 1 strict inequality

Where p1, p2, and p3 are the proportions of responders in the primary endpoint in the placebo group, ALXN2050 120 mg bid group, and ALXN2050 180 mg bid group, respectively.

## 9.2. Sample Size Determination

The study has 3 treatment groups: ALXN2050 180 mg bid, ALXN2050 120 mg bid, and placebo. The goals of this study are to establish proof of concept for the treatment of gMG with ALXN2050 and to select a dosage for further development of ALXN2050 in gMG. Both trend analysis among the 3 treatment groups and differences in proportions of responders between the ALXN2050 180 mg bid group and the placebo group in the primary endpoint are used for sample size determination.

Data from the Argenx ADAPT study and the Momenta Vivacity-MG study were used to estimate the response rate on placebo with background standard-of-care treatment. Based on the data from both studies, the response rate for the placebo group is assumed to be 25%. A sample size of 54 evaluable participants with a randomization ratio of 1:1 to the placebo group and the ALXN2050 180 mg bid group results in approximately 80% power to detect a treatment effect (difference in the proportions of responders) of 35% between the 2 treatment groups, using a 2-sided type I error rate of 0.1 and the exact binomial computation method. An additional 13 evaluable participants will be enrolled to the ALXN2050 120 mg bid group, for a total of 67 evaluable participants.

Assuming that the response rate for the ALXN2050 120 mg bid group is 45%, with a total of 67 evaluable participants, the study has approximately 80% power to detect the increasing trend in the proportions of responders, using Cochran Armitage test at a 2-sided type I error rate of 0.1.

Assuming about 5% non-evaluability, the study is planned to enroll 70 participants in total.

The sample size calculations were performed in PASS 2020.

## 9.3. **Populations for Analyses**

For the purpose of analyses, the following populations are defined. The primary efficacy analyses will be based on the FAS and safety analyses will be based on the SS.

Population	Description
Randomized Set	All randomized participants grouped by randomized treatment group.
FAS	All randomized participants who receive at least 1 dose of study intervention and have a baseline and at least 1 postbaseline efficacy assessment. Participants will be analyzed as randomized.
PK Analysis Set	All randomized participants who have a baseline PK value and at least 1 evaluable postdose PK assessment.
PD Analysis Set	All randomized participants who have a baseline PD value and at least 1 evaluable postdose PD assessment.
PPS	All participants in the FAS without any important protocol deviations.
SS	All randomized participants who receive at least 1 dose of study intervention. Participants will be analyzed according to the study intervention they actually received.
OLE Set	All randomized participants who receive at least 1 dose of ALXN2050 at the start of the OLE Period.

Abbreviations: FAS = Full Analysis Set; OLE = Open-label Extension; PD = pharmacodynamic; PK = pharmacokinetic; PPS = Per Protocol Set; SS = Safety Set

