4. ANALYSIS SETS

| Analysis Set | Description |
|---------------------------------|---|
| Randomized Set | All randomized participants grouped by randomized treatment group. |
| Re-randomized Set | All re-randomized placebo arm (Group 3) participants grouped by re- randomized treatment group. |
| Full Analysis Set (FAS) | All randomized participants who received at least 1 dose of the study intervention and have a baseline and at least 1 postbaseline efficacy assessment. Participants will be analyzed as randomized. |
| PK Analysis Set | All randomized participants who have a baseline PK assessment and at least 1 evaluable postdose PK assessment. |
| PD Analysis Set | All randomized participants who have a baseline PD assessment and at least 1 evaluable postdose PD assessment. |
| Per Protocol Set (PPS) | All participants in the FAS without important protocol deviations. See Section 6.2.2 for the list of important protocol deviations. |
| Safety Set (SS) | All randomized participants who received at least 1 dose of the study intervention. Participants will be analyzed according to the study intervention they actually received. (Study intervention received is the same as planned study intervention if the participant has received at least 1 dose of planned study intervention. If planned study intervention is not received at all, the most frequently received study intervention will be the received study intervention). |
| ALXN2050-Treated Set | All randomized participants who received at least 1 dose of the ALXN2050. Participants will be analyzed according to the study intervention they actually received. (Study intervention received is the same as planned study intervention if the participant has received at least 1 dose of planned study intervention. If planned study intervention is not received at all, the most frequently received study intervention will be the received study intervention). |
| Open-label Extension Set (OLES) | All randomized participants who received at least 1 dose of ALXN2050 during the OLE Period. |

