5.3. Primary Endpoints Analyses

The primary efficacy endpoint analysis will be performed based on the FAS. The PPS will also be used as a supplementary analysis of the primary endpoint. A sensitivity analysis will be performed by implementing participant-level imputation using the FAS. The supplementary analysis based on a logistic regression model will be additionally performed using the FAS. The primary endpoint analysis will be performed at the first analysis (Week 8).

The details of the statistical analyses of the primary endpoint are provided in the following sections and in Table 1.

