5.3.1. Primary Endpoint

The primary endpoint is the proportion of participants with an MG-ADL total score reduction of ≥ 2 points from the Baseline in any 4 consecutive weeks during the first 8 weeks and who did not receive rescue therapy. To compute this, change from Baseline in the MG-ADL total score at each post-Baseline Visit of the first 8 weeks will be derived, where baseline is defined as the last nonmissing assessment prior to the first dose of study intervention. In general, this baseline assessment will be the Day 1 assessment. If the Day 1 assessment is missing, the latest observation during the Screening Period, where available, will be used as the baseline assessment.

Participants who discontinued early without achieving an MG-ADL total score reduction of ≥ 2 points from the Baseline in any 4 consecutive weeks during the first 8 weeks will be considered as nonresponders. Participants who received rescue therapy anytime during the first 8 weeks will be considered as nonresponders.

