5.3.2. Main Analytical Approach

5.3.2.1. Primary Analysis for the Primary Endpoint

The differences in proportions, along with 2-sided 90% confidence intervals (CIs) using Chan and Zhang method (Chan, 1999), will be presented between the ALXN2050 180 mg bid group and the placebo group. P-value using the Barnard's unconditional exact test to determine whether there is a difference in the proportions of responders between the 2 treatment groups will be presented. No imputation will be implemented.

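### The FAS requirement for a postbaseline assessment drops unassessed early dropouts from the primary denominator, although the endpoint rule already makes them nonresponders

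*Protocol*

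**What the plan says.** Protocol 9.3 limits the FAS to randomised participants who took at least one dose and "have a baseline and at least 1 postbaseline efficacy assessment". SAP 4 keeps the same condition: "intervention and have a baseline and at least 1 postbaseline efficacy assessment. Participants will be analyzed as randomized". SAP 5.3 ties the primary analysis to this set: "The primary efficacy endpoint analysis will be performed based on the FAS".

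SAP 5.3.1 then gives the outcome rule. "Participants who discontinued early without achieving an MG-ADL total score reduction of" at least 2 points "in any 4 consecutive weeks during the first 8 weeks will be considered as nonresponders". Anyone given rescue therapy in the first 8 weeks is also a nonresponder. Table 1 of the SAP repeats both rules. For the primary analysis SAP 5.3.2.1 adds: "No imputation will be implemented".

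The supporting analyses start from the same set. SAP 5.3 says: "A sensitivity analysis will be performed by implementing participant-level imputation using the FAS". The logistic regression in SAP 5.3.4 also uses the FAS, and Protocol 9.3 defines the Per Protocol Set as "All participants in the FAS without any important protocol deviations".

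**The concern.** The endpoint rule and the analysis set do not fit together. Under SAP 5.3.1, a participant who stops before any postbaseline score already has a defined outcome, namely failure. The FAS removes that participant before the rule can act. Someone who leaves on Day 5 unassessed disappears, while someone who leaves just after the Day 8 visit counts as a failure.

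Whether a participant is assessed is a post-randomisation event, and treatment can influence it. Protocol 7.1 lists hypersensitivity, seizure and unacceptable adverse events among the reasons to consider stopping, and a participant who stops study drug permanently should leave the study. Everyone removed this way would have been a nonresponder, so removal can only raise the observed response rate of the arm that loses them. At stake is the comparison of 180 mg with placebo, on which the proof-of-concept reading rests.

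**Working it through.** **Who is removed.** Protocol Table 2 schedules MG-ADL and QMG weekly from Day 8, and also at the Early Discontinuation and Clinical Deterioration visits. Any one of these keeps a participant in the FAS. The FAS asks for an efficacy assessment, not specifically MG-ADL, so a single QMG is enough. The removed group is therefore those dosed, gone before Day 8, and with no Early Discontinuation, Clinical Deterioration or other postbaseline assessment. A participant rescued before a first assessment and not assessed afterwards is lost in the same way.

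**Whether another analysis restores them.**

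| Set or analysis | Restores them to an efficacy analysis? |
|---|---|
| Imputation sensitivity analysis, logistic regression | No, both use the FAS |
| Per Protocol Set | No, it is a subset of the FAS |
| Randomized Set, Safety Set | They are members, but no efficacy analysis uses these sets |
| SAP addendum for the final analysis | No, it drops the sensitivity and supplementary analyses |

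**The plan's own figure.** Inputs from Protocol 9.2: 27 per arm, 25% against 60%, two-sided 0.10. Enumerating all binomial outcomes with a two-sided Barnard test (pooled z statistic, maximised over a 999-point grid for the common rate) gives power of 81.2%. The stated value is approximately 80%, so the sample size reproduces.

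**Shift in the observed rate from one removal.** The change is x/(n − 1) − x/n, with x responders among n. Planned arms are 28/14/28, from 2:1:2 of 70.
- Active arm near 55%: 15/27 − 15/28 = 55.6% − 53.6% = 2.0 points.
- Placebo at the planned 25%: 7/27 − 7/28 = 25.9% − 25.0% = 0.9 points.

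**Effect on the p-value.** The counts are illustrative, because the documents give no number of such dropouts.

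| 180 mg against placebo | All 28 counted | One removed from 180 mg | Crosses 0.10? |
|---|---|---|---|
| 14 against 9 | 0.236 | 0.158 | No |
| 15 against 9 | 0.121 | 0.096 | Yes |
| 16 against 9 | 0.070 | 0.058 | No |
| 13 against 7 | 0.114 | 0.081 | Yes |
| 17 against 7 (about the design rates) | 0.008 | 0.005 | No |

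A removal from placebo works the other way: 15/28 against 9/27 gives p = 0.141, up from 0.121.

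**How often the verdict changes.** Suppose exactly one unassessed dropout, on 180 mg, so 27 assessed plus 1 failure against 28 on placebo. Over all outcomes, the finding in favour of 180 mg changes in 5.9% of trials at 60% against 25%, and in 0.9% when both rates are 25%.

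**False findings.** Let the true rate over all 28 treated be 25% in both arms, and let k failures be removed from 180 mg only. The rate among those assessed is then 0.25 × 28/(28 − k). The chance of a finding favouring 180 mg is 5.3%, 6.1% or 8.2% for k = 1, 2 or 3, against 4.1% to 4.2% when they count as nonresponders.

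**The case against.** The strongest reply is that the group is very small. Visits are weekly, and Protocol 7.2 asks for an Early Discontinuation Visit where it can be done. A participant who leaves before Day 8 but attends it stays in the FAS as a nonresponder. This stands. A reader might infer that every dropout before the first weekly visit is removed, but Table 2 does not support that. The visit is not guaranteed, however, so a gap remains.

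Second, the examples that cross the threshold lie just above 0.10, and neighbouring tables and the design-rate table do not cross. This also stands. A reader might infer that one removal is enough to decide the trial. It can be, but only in a close result. The 8.2% figure needs three such dropouts, all on 180 mg and none on placebo.

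Third, the direction is not known in advance, since losses on placebo work against ALXN2050. That is correct, and the point should not be read as a bias that always favours the drug.

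Fourth, SAP 5.2 tabulates and lists membership of each set and the discontinuations with reasons, so a reader could redo the count. That makes the problem visible. It does not put a corrected analysis into the plan.

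Finally, Protocol 9 calls all results exploratory, and the SAP addendum reports termination for lack of efficacy at Week 8. The documents therefore give no ground for inferring that the exclusion produced a positive conclusion. These facts limit the weight of the point but do not reconcile the two rules.

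**Conclusion.** The point holds in a narrow form. The FAS condition conflicts with the plan's own nonresponder rule, and it removes from the primary denominator dosed participants who left before Day 8 without any postbaseline assessment. No planned efficacy analysis restores them. The size is about 2 points per removal for an active arm near 55% and about 1 point for placebo near 25%. One removal can change the verdict near 0.10 but usually does not.

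This rests on two assumptions. The dropout counts are illustrative, and the Barnard test uses the pooled z ordering. The stated sample size is not in question. A reader might equate the 5% non-evaluability allowance (70 enrolled against 67 evaluable, a difference of 3) with FAS exclusions, but the documents do not define evaluable, so that link cannot be made.

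**What to change.** For the primary endpoint and the other endpoints based on any 4 consecutive weeks in the first 8 without rescue (SAP 5.4.1.6, 5.4.1.7 and the dual-responder endpoint in 5.5.1.1), analyse all randomised participants who received at least one dose, as randomised. Count those with no postbaseline assessment as nonresponders. State this in Protocol 9.3 and SAP 4, and in SAP Tables 1 and 2.

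Leave the MMRM unchanged. Also leave the Week 8 responder endpoints unchanged: SAP Table 2 restricts them to participants with a nonmissing assessment at that visit, and a rule covering every responder endpoint would contradict it.

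The cost is a few lines of text. Observed response rates may be slightly lower, and the denominators of the 4-week and Week 8 endpoints may differ slightly. At 28 against 28, Barnard power is 83.3% with no such dropouts. It is 79.9% if 5% of each arm become nonresponders (0.95 × 25% = 23.75% against 0.95 × 60% = 57.0%), still about the planned 80%. If 1, 2 or 3 such dropouts all fell on 180 mg, power would be 79.0%, 74.1% or 68.5%.

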## 9.4. Statistical Analyses

## 9.4.1. Enrollment and Disposition

The number of participants screened, screen failed, and randomized will be presented. Enrollment information will be grouped by stratification factor and treatment allocation. The number of participants discontinued (along with reasons) from the PEP, ETP, OLE Period, and the overall study will be summarized.

## 9.4.2. Demographics, Baseline Characteristics, Inclusion and Exclusion Criteria, and Protocol Deviations

All demographic information and baseline characteristics will be reported by treatment group and overall. No statistical test will be performed for homogeneity among treatment groups.

The number and percentage of participants not meeting a specific inclusion or exclusion criterion will be summarized. A similar summary will be provided for important protocol deviations based on prespecified categories.

## 9.4.3. Medical/Surgical History, Physical Examination, and Myasthenia Gravis History

Medical and surgical history will be summarized using the Medical Dictionary for Regulatory Activities (MedDRA), Version 23 or later, System Organ Class (SOC) and Preferred Term. Myasthenia gravis history and abnormal physical examination findings will also be summarized.

## 9.4.4. Prior and Concomitant Medications

For analysis and reporting purposes, any medication started prior to first dose of study intervention will be considered prior medication, and medications that were received on or after the first dose of study intervention will be considered concomitant medications. All prior and concomitant medications including MG-specific medications and rescue therapy during the study, if any, will be summarized.

## 9.4.5. Extent of Drug Exposure

The cumulative and total drug exposure, dose intensity and relative dose intensity, and treatment duration will be summarized by treatment group and study periods. The relative dose intensity will be calculated as the percentage of the actual drug exposure divided by the protocol planned drug exposure by study period.

## 9.4.6. Efficacy Analyses

All efficacy analyses will be based on the FAS. Supplemental per-protocol analyses for primary and secondary efficacy endpoints will be performed based on the PPS in the same manner as the FAS.

## 9.4.6.1. Analyses of Primary Efficacy Endpoint

## 9.4.6.1.1. Primary Analysis for the Primary Endpoint

The primary endpoint is the proportion of participants with an MG-ADL total score reduction of  $\geq 2$  points in any 4 consecutive weeks during the first 8 weeks and who did not receive rescue therapy.

The differences in proportions, along with 2-sided 90% confidence intervals (CIs) using Chan and Zhang method (Chan, 1999), will be presented between the ALXN2050 180 mg bid group and the placebo group. P-value using Barnard's unconditional exact test to determine whether there is a difference in the proportions of responders between the 2 treatment groups will be presented.

## 9.4.6.1.2. Secondary Analysis for the Primary Endpoint

The differences in proportions, along with 2-sided 90% CIs using Chan and Zhang method (Chan, 1999), will be presented for the following pairwise comparisons: between the ALXN2050 120 mg bid group and the placebo group, and between the ALXN2050 180 mg bid group and the ALXN2050 120 mg bid group.

In addition, the proportions of responders in each treatment group will be presented along with exact 2-sided 90% CIs using the Clopper-Pearson method.

Trend analysis to detect whether there is an increasing trend in the proportions of responders in the primary endpoint will be presented along with the p-value using Cochran Armitage test.

## 9.4.6.2. Analyses of Secondary Efficacy Endpoints

For all continuous secondary endpoints (QMG total score, MG-ADL total score, Neuro-QoL™ Fatigue score) related to the change from baseline at Week 8, the mixed-effects model with repeated measures (MMRM) will be used to estimate the treatment effect using all available data, irrespective of whether participants received rescue therapy. Missing data will not be imputed for the analysis. For each of the continuous secondary endpoints, the MMRM will include change from baseline at each prespecified time point as the response variable, treatment group, study visit, and treatment-by-study visit interaction as fixed categorical effects, and baseline total score as a covariate. The treatment effect will be evaluated via contrast for the treatment-by-visit term at Week 8. An unstructured covariance matrix will be used to model the correlations among repeated measurements within each participant. Other covariance structures will be implemented if a convergence issue occurs (details to be provided in the SAP). The Kenward-Rogers method will be used to estimate the denominator degrees of freedom.

Trend analysis to detect whether there is a decreasing trend in the change from baseline at Week 8 in MG-ADL total score will be presented along with the p-value using Jonckheere-Terpstra trend test.

For the categorical secondary endpoints:

• Proportion of participants with at least a 3-, 4-, 5-, 6-, 7-, or 8-point improvement in the QMG score at Week 8

- Proportion of participants with a QMG score reduction of  $\geq$  3 points in any 4 consecutive weeks during the first 8 weeks and who did not receive rescue therapy
- Proportion of participants with at least a 2-, 3-, 4-, 5-, 6-, 7-, or 8-point improvement in the MG-ADL total score at Week 8
- Proportion of participants with at least a 3-, 4-, 5-, 6-, 7-, or 8-point improvement in the MG-ADL total score in any 4 consecutive weeks during the first 8 weeks and who did not receive rescue therapy
- Proportion of participants with at least a 4-, 5-, 6-, 7-, or 8-point improvement in the QMG total score in any 4 consecutive weeks during the first 8 weeks and who did not receive rescue therapy

The proportions of responders in each treatment group will be presented along with exact 2-sided 90% CIs using Clopper-Pearson method. The differences in proportions between each of the ALXN2050 dosage groups (180 mg bid or 120 mg bid) and the placebo group will be presented, along with 2-sided 90% CIs using Chan and Zhang method (Chan, 1999).

